# Sensitivity analysis

The primary endpoint analysis will be re-run with the PP population as a sensitivity analysis. Secondary endpoints.

Coefficient of variation will be reported for each group: bootstrap methods will be used to estimate variability as appropriate.

Rates of hospitalisations for severe hypoglycaemia and moderate hypoglycaemia as per participant log will be analysed as unadjusted incidence rates based on the Poisson distribution. Incidence rates and incidence rate differences will be presented with their associated 95% confidence intervals calculated as exact Poisson confidence limits(22). In addition, where

HCL outpatient Version Number:6.0 Version Date:15/07/2019 appropriate Poisson or negative binomial regression models will be fitted e.g. moderate hypoglycaemia events from the participant log. If there are a high proportion of zero counts, zero inflated Poisson (ZIP) or zero inflated negative binomial models (ZINB) will be considered. If counts are sparse then rates will be reported descriptively only. Number of hospitalisations due to diabetic ketoacidosis events and other safety outcomes will be tabulated and presented as n and %.

Continuous outcome measures (including psychosocial) collected at baseline and endpoint will be analysed using ANCOVA adjusting for baseline score and site. Measures collected at baseline, 3 months and endpoint (e.g. *HbA1c*, *Fasting capillary blood glucose*, *Mean CGM glucose*, *Hypoglycaemic Fear Survey-II Worry scale*, *Child State-Trait Anxiety Inventory*, *The Diabetes Treatment Satisfaction Questionnaire status and change version*, *Problem Areas in Diabetes, Impaired awareness of hypoglycaemia: GOLD SCORE, INSPIRE questionnaires*) will be analysed using mixed models repeated measures (MMRM) adjusting for baseline score (where appropriate), group, period (baseline, 3 months, 6 months) and site. A random intercept term for 'individual' will also be employed if deemed appropriate. Least square means and least square mean differences and their associated 95% confidence intervals will be presented for each group and between groups. Unstructured covariance matrix will be used unless other covariance structures are more appropriate as determined by the Bayesian information criteria (BIC). Human technology interaction and health care professional experiences and expectations analyses will be reported Exploratory; descriptive analysis.

A separate economic analysis will be conducted. Using measures (e.g. QALYs calculated from the EQ-5D) collected during the trial.

Performance Parameters will be reported descriptively (n, % for categorical measures and n, mean, median, standard deviation, minimum and maximum for continuous measures)

Subgroup and exploratory analysis

Subgroup analysis will be performed to examine differences in treatment effect based on participant characteristics. Subgroup analysis will be treated as exploratory, with the intent of hypothesis generation. A treatment by subgroup interaction term will be included in the MMRM to assess differential effects by subgroup. Subgroup analyses may include (but not be limited to):

- Age
  - o <12 years
  - $\circ$  >12 years
- BMI category
  - 0 <18
  - $\circ$  18 25
  - o > 25
- Diabetes duration
  - o <6 years
  - o 6 years or longer
- HbA1c at baseline.
  - 0 <8%
  - o 8% or greater

A range of additional exploratory analyses will be conducted. These analyses may include (but not be limited to):

- Differential effects of intervention based on time of day
- Examination of time spent in various glycaemic ranges
- Finer-grained analysis of BGL patterns
- Relationship between CGM usage/adherence and outcomes
- Differences in effect size based on control treatment regimen

Techniques used for subgroup and exploratory analysis will depend upon the distribution of the outcome measure and will include presentation/comparison of unadjusted rates with Poisson confidences limits (or negative binomial models where overdispersion is indicated), measures of central tendency and dispersion, mixed modelling, analysis of covariance, and novel graphical presentation.

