## 3. Psychosocial:

Assess the average difference between standard therapy (MDI and CSII) in the following measures:

- i. **Fear of hypoglycaemia**: Hypoglycaemic Fear Survey-II Worry scale: 17-<25years. Children's Hypoglycaemia Fear survey 12 17 years.
- ii. **Hypoglycaemia Awareness**: Hypoglycaemia Awareness Scale (Gold Score) (all ages)
- iii. **Anxiety**: State-Trait Anxiety Inventory (Child version for 12-15yrs, adult version ≥16-<25yrs)
- iv. **Impact and Satisfaction**: The Diabetes Treatment Satisfaction Questionnaire status and change version (16 <25 years)
- v. **Quality of Life**: 12-<25years: EQ-5D-Y,
- vi. **Diabetes specific quality of life**: PedsQL Child version (12 years) Adolescent version (13 18 years) and young adult version (18 <math><25 years).
- vii. **Diabetes distress:** Problem Areas in Diabetes (Teen version for 12 17 years, standard version  $\geq 17 \langle 25yr \rangle$
- viii. **Participant reported outcome for Automated Delivery system:** INSPIRE Questionnaires: baseline and post-assessment versions Child version (12 year olds), Adolescent version (13-18) and adult version(18-25)
- ix. **Semi structure interview** (all ages post study, PCH only)

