## 15.2Fear of Hypoglycaemia

### Fear of Hypoglycaemia Survey (worry scale) (Ages >17 years)

Below is a list of concerns people with diabetes sometimes have about low blood sugar. Please read each item carefully (do not skip any). Tick the box that best describes how often in **the last 6 months** you WORRIED about each item because of low blood sugar.

	ause my blood sugar could go low, l ried about	Never	Rarely	Sometime	s Often	Almost always
1.	not recognising / realising I was having low					
	blood sugar					
2.	not having food, fruit or juice available					
3.	passing out in public					
4.	embarrassing myself or my friends in a social situation	I 🗌				
5.	having a hypoglycaemic episode while alone					
6.	appearing stupid or drunk					
7.	losing control					
8.	no-one being around to help me during a					
	hypoglycaemic episode					
9.	having a hypoglycaemic episode while driving					
10.	making a mistake or having an accident					
11.	getting a bad evaluation or being criticised					
12.	difficulty thinking clearly when responsible for others	r 🔲				
13.	feeling lightheaded or dizzy					
14.	accidentally injuring myself or others					
15.	permanent injury or damage to my health or					
4.0	body					
16.	low blood sugar interfering with important things I am doing					
17.	becoming hypoglycaemic during sleep					

HCL outpatient Version Number:6.0 Version Date:15/07/2019

18.	getting emotionally upset and difficult to deal with		Ш		
Fear	of Hypoglycaemia Survey (FHS) © Gonder-Frederic	k L, 1994			

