### 15.3General Anxiety

STAI adult (17 years and older)

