## 15.6Treatment Satisfaction

Pa	rticipant ID:	Pa	artici	oant l	OOB:	/_	/_	_	Date://
	Diabetes Treatm	ent Sa	tisfa	ctio	n Qu	estic	onna	ire (c	hange): DTSQc
dur pre Ple	the past few weeks you led a change of treatment. To ing the past 5 days has devious 5 days. (Treatment ase answer each question to have experienced change	have been day we changed includes by circli	en tak would from medi	ing pa like to your e cation	art in a know experie and o	diabe how ence diet).	etes tr your e	eatmer experier r usual	nt study. Five days ago yo nce of this current treatmer pump treatment during th
1.	How satisfied are you w	ith your	currer	nt trea	tment?	?			
	much more satisfied now	3	2	1	0	-1	-2	-3	much less satisfied now
2.	How often have you felt	that you	r bloo	d suga	ars ha	ve bee	en una	ccepta	bly high recently?
	much more of the time now	3	2	1	0	-1	-2	-3	much less of the time now
3.	How often have you felt	that you	r bloo	d suga	ars ha	ve bee	en una	ccepta	bly low recently?
	much more of the time now	3	2	1	0	-1	-2	-3	much less of the time now
4.	How convenient have yo	u found	your t	reatm	ent to	be red	cently?	?	
	much more convenient now	3	2	1	0	-1	-2	-3	much less convenient now
5.	How flexible have you fo	und you	r treat	ment	to be r	ecent	ly?		
	much more flexible now	3	2	1	0	-1	-2	-3	much less flexible now
6.	How satisfied are you wit	th your u	ınders	tandir	ng of y	our di	abetes	?	
	much more satisfied now	3	2	1	0	-1	-2	-3	much less satisfied now
7.	Would you recommend to	his form	of trea	atmen	t to so	meon	e else	with yo	our kind of diabetes?
	much more likely to recommend the treatment now	3	2	1	0	-1	-2	-3	much less likely to recommend the treatment now
3.	How satisfied would you	be to co	ntinue	with y	our p	resent	form	of treat	ment?
	much more satisfied now	3	2	1	0	-1	-2	-3	much less satisfied now
	Please make sure	that you	have	circl	ed on	e num	ber o	n each	of the scales.

DTSQs © [name] 9/93. English for Australia 11.8.06 (from standard UK English rev. 7/94)

Health Psychology Research Unit, Royal Holloway, University of London, Egharn, Surrey, TW20 0EX, UK. For use under licence HPR1465

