## **INSPIRE** Questionnaire for Teenagers with Type 1 Diabetes (Post Assessment)

We would like ask about your thoughts and feelings about your experience using an automated insulin delivery system (abbreviated AID), sometimes called a closed loop system, artificial pancreas or bionic pancreas. We would like you to think about living with diabetes and the things that may have been better or worse by using AID. For each of the questions below, please tick (check) the box that best fits your answer. Please answer every question.

1 I worried less about diabetes with the AID.	
diabetes.  3 AID made it easier for me do the things that I wanted to do without diabetes getting in the way.  4 AID decreased how often I had low glucose levels.  5 AID decreased how often I had high glucose levels.  6 AID helped me stay in my target glucose range more often.  7 AID improved my A1c to target level.	
wanted to do without diabetes getting in the way.  4 AID decreased how often I had low glucose levels.  5 AID decreased how often I had high glucose levels.  6 AID helped me stay in my target glucose range more often.  7 AID improved my A1c to target level.	
levels.   5 AID decreased how often I had high glucose	
levels.  6 AID helped me stay in my target glucose range more often.  7 AID improved my A1c to target level.  8 AID made it easier to eat when I wanted to.	
more often.  7 AID improved my A1c to target level.  8 AID made it easier to eat when I wanted to.  9 AID made it easier to exercise when I wanted to.	
8 AID made it easier to eat when I wanted to.	
AID made it easier to exercise when I wanted to.	
Alb made it edistri to exercise when I wanted to.	
Strongly Agree Neither Disagree Strongly Agree Opisagree Disagree Disagree	N/A
AID made managing diabetes easier when I was	
11 AID made managing diabetes easier when driving	
12 AID made managing diabetes easier when it came to my social life/being with friends.	
AID helped me manage sick days.	
14 AID reduced my risk of long term complications.	
Strongly Agree Neither Disagree Strongly Agree Agree nor Disagree Disagree	N/A
AID helped me sleep better.	
16 I had fewer lows during the night with AID.	
AID improved my overall quality of life.	
18 AID improved my family's overall quality of life.	

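### INSPIRE is placed in a between-arm repeated-measures model, but its post-assessment form gives controls nothing scorable and the 13-week visit list omits it; the DTSQ change form and the STAI and PAID age bands also need reconciling

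*Protocol*

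**What the plan says.** Section 7.3, in the secondary-endpoint text under the heading Sensitivity analysis, names the measures collected at baseline, 3 months and endpoint. The list includes "The Diabetes Treatment Satisfaction Questionnaire status and change version" and "Impaired awareness of hypoglycaemia: GOLD SCORE, INSPIRE questionnaires". These go into an MMRM with group, period (baseline, 3 months, 6 months) and site, plus the baseline score where appropriate. The output is specified: "Least square means and least square mean differences and their associated 95% confidence intervals will be presented for each group and between groups".

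The synopsis and section 6.2.2 say questionnaires are given at baseline, 13 weeks and 26 weeks, and list INSPIRE among them. The visit descriptions list INSPIRE at Visit 1 and Visit 16 only. Section 7.1 keeps the conventional arm on MDI or CSII for 6 months.

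The forms are printed in the appendices. A typical INSPIRE post-assessment item is "AID decreased how often I had low glucose" levels (appendix 15.8). The DTSQ change form (appendix 15.6) opens with a reference to taking part in a treatment "study. Five days ago yo" and so on. For anxiety, section 6.3 gives "State-Trait Anxiety Inventory (Child version for 12-15yrs, adult version ≥16-<25yrs", while appendix 15.3 heads its form "STAI adult (17 years and older".

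**The concern.** A between-arm least square mean difference needs a score on the same scale in both arms. The INSPIRE post-assessment form presupposes that the respondent has used the system under test. If it is analysed as written, the control mean is either missing or built from answers about a device the respondent did not use. Nor can the model lean on the baseline value, because the baseline form measures something else. Data collected on a form that does not apply cannot be recovered by analysis.

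The other two points are of the same kind but smaller. A change questionnaire with the wrong reference period measures the wrong change. Conflicting age bands leave sites to choose the form, and a participant may be scored on different scales at baseline and week 26.

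**Working it through.** No sample size or error-rate figure underlies this point. The check sets the forms, the visit lists and the analysis text side by side.

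**INSPIRE.** The model has 2 arms × 3 occasions = 6 cells. What each cell can hold:

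| Occasion | HCL arm | Control arm |
|---|---|---|
| Baseline (Visit 1) | expectations of automated delivery | expectations of automated delivery |
| 13 weeks (Visit 11) | not on the visit list | not on the visit list |
| 26 weeks (Visit 16) | experience of automated delivery | N/A only |

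Two cells are empty on the visit list and one is unscorable, so 6 − 2 − 1 = 3 remain. Two of those three are baseline expectation scores. One cell carries experience data, and one cell gives no contrast between arms. The adult form also changes from 22 items at baseline to 21 at post-assessment (the pregnancy item has no counterpart); the teen and child forms have 18 items each time.

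Nothing in the protocol limits INSPIRE to the HCL arm. Where the protocol does mean HCL users only, it says so: appendix 15.9 has a separate set of app questions for closed-loop users. Numbers affected: up to 80 enrolled controls, or 80 × (1 − 0.20) = 64 after the drop-out allowed for in section 7.2.

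**DTSQ change form.** The printed lead-in places the change of treatment five days back and compares it with usual pump treatment in the five days before. In this trial:
- the form is listed at Visits 11 and 16, that is weeks 13 and 26;
- MDI users, eligible under section 7.4.1, have no usual pump treatment;
- controls have had no change of treatment;
- it is also listed at Visit 1, before anyone has changed, so a baseline value of change does not exist.

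The DTSQ status form has none of these faults.

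**Age bands.**

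| Instrument | Body (6.2.2, 6.3) | Appendix | At age 16 |
|---|---|---|---|
| STAI | child 12–15, adult from 16 | child 12–16, adult from 17 | adult v child |
| PAID | teen 12–17, standard from 17 | teen 12–16, standard from 16 | teen v both |

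The versions are not interchangeable. STAI items have four response categories in the adult form and three in the child form. PAID has 20 items in the standard form and 27 printed in the teen form, of which items 22 and 27 are identical.

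The protocol gives no age distribution, so the number affected is an assumption. With ages spread evenly over the 13 yearly ages from 12 to 24, 160 / 13 ≈ 12 participants are aged 16. If that share were 5% to 15%, the number would be 160 × 0.05 = 8 to 160 × 0.15 = 24. Separately, over a 7-month study about 7/12 of those in the year below any one cut would cross it: 12.3 × 7/12 ≈ 7 with even ages, or about 5 to 14 across the same range of shares.

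**The case against.** Several counter-arguments carry weight.

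- Every INSPIRE post form has an N/A column, so controls can complete it. That stands: the fault is that they have no scorable answer, not that they have no answer.
- The synopsis and section 6.2.2 do place INSPIRE at 13 weeks, so its absence at Visit 11 may be a slip in the visit list. Section 7.3 also provides ANCOVA for measures taken only at baseline and endpoint. The missing 13-week value alone would therefore break little. The week-26 control cell remains the problem under either model.
- The appendix copy of the DTSQ status form is marked as for information, so the printed change form may also be a specimen, and its text is badly scrambled by extraction. The change version is also named at Visit 1 through a combined label repeated in every list. Adjustment for baseline is required only where appropriate. This reduces the DTSQ point to a correction of wording and timing, but the printed form is the only one in the protocol and it does not fit this trial.
- Age is a stratification factor and both arms use the same forms, so the age conflicts do not bias the randomised comparison. Agreed.

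A reader might infer more than the documents support. Hypothesis 4 does not stand or fall with these forms: it names quality of life and fear of hypoglycaemia, whereas INSPIRE, DTSQ, STAI and PAID are separate endpoints. The adult fear survey asks about "the last 6 months", and it is tempting to conclude that its week-13 effect is halved. That would need respondents to average evenly over the recalled weeks, which nothing in the protocol supports; it concerns an intermediate visit, and week 26 is collected. The apparent gap or overlap between the fear surveys at age 17 depends on how the upper limits are read.

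**Conclusion.** The INSPIRE fault is real. As written, section 7.3 promises a between-group difference that cannot be formed, because up to all 80 controls have no scorable post-assessment value and the baseline form measures expectations. This rests on controls not using automated delivery during the trial and on the printed forms being those administered.

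The DTSQ change form is a secondary point: its printed reference period and comparator do not fit weeks 13 and 26, MDI users or controls, and it has no place at Visit 1. The STAI and PAID age conflicts are also secondary. They leave the form undetermined at age 16, for about 12 participants if ages are even (8 to 24 over the assumed range), and add noise rather than bias between arms.

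A reader might infer that the psychosocial comparison as a whole fails. It does not: DTSQ status, EQ-5D-Y, PedsQL and the Gold score are not undermined by the faults described here, and the primary endpoint is unaffected. The changes should be made because they are cheap and cannot be made once the data are in.

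**What to change.** - **INSPIRE:** give the post-assessment form to the HCL arm only, report it descriptively, remove INSPIRE from the MMRM list in section 7.3, and reconcile the synopsis and section 6.2.2 with the Visit 11 list on whether it is given at 13 weeks.
- **DTSQ change form:** delete it from Visit 1 and from any baseline term, keep it at weeks 13 and 26, and align its lead-in with this trial, so that the comparison is with treatment before joining the study. Keep the status form as it is.
- **STAI and PAID:** state one non-overlapping age cut per instrument, the same in body and appendix. Assign the version by age at Visit 1 and keep it to week 26, so that baseline and follow-up use the same scale. Age at randomisation would not do, because the Visit 1 forms are completed before it.

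The cost is an amendment to protocol and form wording, plus the licence holder's agreement to the changed DTSQ lead-in. Sample size and the primary analysis do not change.

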## 7.4 Inclusion and exclusion criteria

## 7.4.1. Inclusion criteria:

- 1. Type 1 diabetes (diagnosis consistent with American Diabetes Association Classification of Diabetes Mellitus) diagnosed at least 1 year ago
- 2. Fasting C-peptide <0.1 nmol/L (in the absence of hypoglycaemia) within the last 3 months
- 3. Insulin regimen either:
  - Multiple daily injections (MDI) with  $\geq 4$  injections per day ( $\geq 3$  rapid-acting insulin and ≥1 long-acting insulin); or
  - Insulin pump therapy (CSII) established for  $\geq 3$  months
- 4. Aged 12-<25 years
- 5. HbA1c ≤10.5%
- 6. Living in an area with internet and cellular phone coverage
- 7. English speaking

## 7.4.2 Exclusion Criteria

A subject is excluded from the study if any of the following criteria are met:

- 1. Chronic kidney disease (eGFR <45mL/min/1.73m^2)
- 2. Use of any non-insulin glucose-lowering agent within the past 3 months
- 3. Oral or injected steroid use within the past 3 months
- 4. Pregnancy, or planned pregnancy within study period
- 5. Uncontrolled coeliac disease (not following a gluten free diet), or other untreated malabsorption
- 6. Uncontrolled thyroid disease
- 7. Clinically-significant gastroparesis
- 8. Uncontrolled hypertension (DBP >100 mmHg and/or SBP >160 mmHg)
- 9. History of myocardial infarction, severe uncontrolled heart failure, unstable angina, transient ischaemic attack (TIA), stroke, or thromboembolic disease in the past 3 months.
- 10. Poor visual acuity precluding use of the investigational technology
- 11. Inability or unwillingness to meet protocol requirements (including carbohydrate-counting, CGM use as per allocated study group only).
- 12. Severe or unstable medical or psychological condition which, in the opinion of the would compromise the ability protocol requirements investigator, to meet

Visit Schedule	Pre screening																	
CRF visit number		1	2‡	3	4	5	6*	7*‡	8	9	10	11	12	13	14	15	15a#	16ф
Length of time of visit (hours)		4	2 to 8	2	1.5	1.5	4	0.5 to 8	1	1.5	1.5	4	1.5	1.5	1.5	4	1.5	4
Weeks from Randomisation																		
(+/- 2 week window either side of visit)		-4₹	-3 <del>Y</del>	-3	-2	-1	0	0	4	11	12	13	23	24	25	26	26+1	26
Informed Consent		Х																
Auxological data		Х					Χ					Х						Χ
Diabetes clinical history		Х																
C-peptide	x (local)						Х											
U + Es	х																	
bHCG		Х																
HbA1c	х						Х					Х						х
Blood pressure		Х					Х					Х						х
Total Daily Dose		Х					Х					Х						Х
Carbohydrate Counting			Х															
Insulin pump review			Х						Х			Х						
Pump training								Х										
Logbook data recorded				х	Х	Х		х	Х	Х	Х	Х	Х	Х	Х	Х	Х	Χ
logbook data collected							Х					Х				Х	Х	
CGM				х	Х	Х				Х	Х		Х	Х	Х	+/-x	Х	
Psychology measures		Х					Х					Х				Х		
Modified momentary Sampling								Х	Х	Х	Х	Х	Х	Х	Х	Х	х	
Biomarkers							Х											Х
Semi-structured Interview					_										_			Х

Y Length to randomisation may vary according to education level

HCL outpatient Version Number: 6.0 Version Date: 15/07/2019

‡ Length of time and number of visits (2a, 2b...) will depend on baseline management regimen and carbohydrate counting knowledge

\* Variation in requirement depending on randomisation

φ Random selection of participants will be offered semi-structured interview

# only needed if insufficient CGM

#### 7.4 Visit schedule

Pre-screening of HbA1c, eGFR and C-Peptide for eligibility will be required, to occur within 3 months of formal screening.

VISIT 1 4hr. (Screening and Eligibility Check).

Information sheets will be provided in advance to participants who potentially fit inclusion criteria. Participants will be checked if they meet the inclusion criteria listed above. All post menarche females will have a βHCG test to exclude pregnancy. The following data will be recorded:

- 1. Consent signed by participant and investigator
- 2. Demographic
  - a. Date of Birth
  - b. Gender
- 3. Auxological
  - a. Height
  - b. Weight
  - c. BMI
- 4. Diabetes clinical
  - a. Date of diagnosis
  - b. C-peptide (local laboratory value can be used for the purpose of the 0.1nmol/L cut off within 3 month of screening visit, and formal samples will be stored for centralised assay at a later date).
  - c. HbA1c (local laboratory or DCA value can be used for the purpose of the 10.5% cut off)
  - d. βHCG for all post menarche females
  - e. History of severe hypoglycaemia coma or convulsion or requiring help from others (events in last 12 months).
  - f. Seated blood pressure (average of 2 readings)
  - g. Total daily dose of insulin (mean of previous 7 days)
  - h. Carbohydrate ratios and insulin sensitivity factors
  - i. Co-morbidities and medications
  - j. Smoking and alcohol intake
- 5. Psychology measures:

Psychological scales will be on an electronic platform where applicable.

- a) **Fear of hypoglycaemia**: Hypoglycaemic Fear Survey-II Worry scale: 17-<25years. Children's Hypoglycaemia Fear survey 12 17 years.
- b) **Hypoglycaemia Awareness**: Hypoglycaemia Awareness Scale (Gold Score) (all ages)
- c) **Anxiety**: State-Trait Anxiety Inventory (Child version for 12-15yrs, adult version ≥16-<25yrs)
- d) **Impact and Satisfaction**: The Diabetes Treatment Satisfaction Questionnaire status and change version (16 <25years)
- e) Quality of Life: 12-<25 years: EQ-5D-Y,
- f) **Diabetes specific quality of life**: PedsQL Adolescent version (13 18) and young adult version (18 <25).
- g) **Diabetes distress:** Problem Areas in Diabetes (Teen version for 12 17 years, standard version  $\geq 17 \langle 25yrs \rangle$
- h) **Participant reported outcome for Automated Delivery system:** *INSPIRE Questionnaires: baseline and post-assessment versions Child version (12 year olds), Adolescent version (13-18) and adult version(18-25)*

Page 26 of 85

VISIT 2\* (within 4 weeks of Visit 1 run in and education planning)

An individual education program will be planned to occur over the next 2 weeks, and will vary according to the prior knowledge and baseline treatment of that participant.

- i. CSII as baseline treatment
  - a) Carbohydrate Counting: 1 x dietician review (1 -2 hours)
  - b) General pump review:  $1 \times 4$  diabetes educator session (1 4) hours to review pump settings, download capability.
- ii. MDI as baseline treatment
  - a) Carbohydrate Counting: 1-3 x dietician (1 -2 hours) review over a week period (prior to visit 3). This may be extended over a period of 3 weeks if deemed clinically necessary. Participants will be issued with an Aviva Expert (Roche) glucometer and testing strips, which will be programmed with individual carbohydrate ratio, and insulin sensitivity.

